9.6. Data management

This study, which will be conducted based on this common protocol, will use the Vaccine monitoring Collaboration for Europe (VAC4EU, <https://vac4eu.org/>) research environment based on a common protocol, and a common data model (CDM).¹⁶ The work will be conducted using a distributed network of the participating data access providers (DAPs), all of whom have experience and have contributed to the CONSIGN project. The work will proceed according to Model C (Figure 1): each DAP will extract the data required for the study and transform their local patient level data into a CDM. It is proposed to use the ConcePTION CDM, which is publicly available¹⁶ and is being specifically developed for multinational studies of medication safety in pregnancy. Extraction, transformation, and loading (ETL) design and instructions are available, as well as tools to check the quality of the data for the AESI estimated utilized for the ACCESS

background rate protocol. A common program to run quality checks, data transformation, and analysis will be prepared, verified and distributed to all DAPs. Aggregate results and summary estimates resulting from the programs will be returned to the coordinating center for pooled meta-analysis and reporting. The full approach will be developed and described in the Statistical Analysis Plan (SAP).

[figure not shown]

Figure 1. Options for multi-database studies in Europe¹⁷

9.7. Data analysis

The details of the data analysis, including planned tables, figures, and listings for inclusion in the final study report will be provided in the SAP.

9.7.1 Descriptive analyses

Counts and percentages will be presented for categorical variables (age at conception in categories, sex). Means, standard errors, medians and ranges will be presented for continuous variables (age at conception). The proportion of missing data will be described when appropriate. For maternal outcomes, pregnancy will be the unit of observation; for neonatal outcomes, a newborn will be the unit of observation. For the outcomes of congenital malformations and stillbirth the number at risk will be the total number of live or stillborn children.

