9.1. Study design

9.1.1 Prevalence study

The pregnancy complications, adverse pregnancy outcomes (except pregnancy-related death), and neonatal outcomes (except neonatal death) will be addressed using the prevalence study

design. In the routinely collected data, pregnancies are identifiable on the date of pregnancy end, either in a birth or in an abortive outcome. All identifiable pregnancies will be included, and their start and end dates will be estimated based on the first day of the last menstrual period (LMP) or gestational age at end, depending on data availability. Outcomes examined in this design include gestational diabetes, hypertensive disorders of pregnancy, fetal growth restriction/small for gestational age, abortive outcomes, stillbirth, preterm birth, major congenital malformations, microcephaly (head circumference), and ectopic pregnancy..

Risk of adverse and pregnancy outcomes will be compared in births exposed and unexposed to Spikevax. The measure of association will be prevalence ratio.

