9.2.1 Inclusion Criteria

The study population will include all pregnancies, identifiable in the databases, ending in a live or still birth, a spontaneous abortion, an induced abortion, or an ectopic pregnancy, as identifiable in the participating databases during the study period. In Denmark and Norway, all

pregnancies ending in a live or still birth, as well as pregnancies leading to a hospital encounter due to termination will be identifiable. All pregnancies will be eligible for inclusion.

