9.3. Variables

9.3.1 Exposure

The exposure will be defined by a record of receipt of at least one dose of Spikevax during pregnancy.

For the purposes of timing of exposure, trimesters of pregnancy will be defined as follows:

- First trimester: from the first day of the last menstrual period (LMP) to LMP+97 days (both dates inclusive);
- Second trimester: from LMP+98 days to earliest of (LMP+202 days, pregnancy end) (both dates inclusive);
- Third trimester: from LMP+203 days (inclusive) until pregnancy end date (not included)

Pregnancies unexposed to Spikevax vaccine will be categorized as unexposed or as exposed to other COVID-19 vaccines and other non-COVID-19 vaccines (influenza, meningococcal disease, pneumococcal disease, rubella, shingles, tuberculosis), overall and trimester-wise. Pregnancies among women who received Spikevax before LMP will be enumerated and may be used as an additional comparator, group size permitting.

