9.3.2 Outcome

9.3.2.1 Primary outcomes

The following outcomes will be assessed, noting that outcome-specific analytic considerations such as the etiologically relevant exposure window and specific additional population restrictions (e.g., exclusion of women with teratogenic medication exposure or teratogenic infections for assessment of major congenital malformations) will be defined in the SAP.

- Pregnancy complications are:
 - Hypertensive disorders of pregnancy (preeclampsia, eclampsia, gestational hypertension)
 - Gestational diabetes
 - Bleeding during pregnancy
 - Postpartum haemorrhage
 - Pregnancy-related death

- Adverse pregnancy outcomes are:
 - Fetal death (spontaneous abortion or stillbirth)
 - Termination of pregnancy for fetal anomaly (TOPFA)
 - Any elective pregnancy termination
 - Ectopic pregnancy

- Adverse neonatal outcomes are:
 - Fetal growth restriction/small for gestational age (SGA), using sex- and gestational-age specific cutoffs¹³
 - Preterm birth (<37 full gestational weeks)
 - Low birth weight (<2500 g)
 - Major congenital malformations¹⁴
 - Microcephaly (based on head circumference)
 - Low 5-minute Apgar score
 - Neonatal death (death within 28 days of birth)

Where a signal is detected for the outcome of major congenital malformation as a composite, organ system-specific analyses will be conducted. Organ-specific major congenital malformations, according to the EUROCAT¹⁴ classification are:

- Nervous system
- Eye
- Ear, face and neck
- Congenital heart defects
- Respiratory

- Oro-facial clefts
- Digestive system
- Abdominal wall defects
- Urinary
- Genital
- Limb
- Other

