9.3.3 Covariates

The key covariates will include country of residence, calendar year of delivery, pregnant woman's age, smoking, alcohol use (whenever measured), marital status or other available socioeconomic measures, gravidity, parity, placenta previa, caesarean delivery, multifetal pregnancies, prior reproductive history (prior still birth, prior child SGA, prior pregnancy with preeclampsia) selected chronic comorbidities (cardiovascular diseases, respiratory diseases, type 2 and gestational diabetes, cancer, mental-health disorders, and autoimmune diseases [rheumatic diseases, systemic lupus erythematosus, inflammatory bowel disease, multiple sclerosis, type 1 diabetes, thyroid disorders, medication use]), selected medication use, body mass index (BMI), and history of COVID-19 infection

Specific covariates' availability may vary by database and will be described in the SAP.

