9.7.3 Methods to control/assess confounding

Crude and adjusted measures of association will be computed comparing the exposed vs the unexposed (prevalence ratios, risk ratios, mortality rate ratios). Adjustment will be performed by the covariates measured, with LMP as the anchor date. Covariates will be included in the

appropriate regression model: log-binomial regression for prevalences and risks and Cox proportional-hazards regression for incidence rate ratios. Candidate covariates for inclusion in the analyses will vary by database. A propensity-score based adjustment may be considered and will be described in a separate Statistical Analysis Plan. Table 5 shows country-specific availability of the covariates.

Table 5 Proposed candidate covariates and data availability in participating databases

Variable/data type	AVAILABILITY OF DATA IN THE DATABASE (either via diagnosis code or procedure or treatment proxy)				
	DENMARK (NATIONAL REGISTRIES)	ITALY/ARS TOSCANA	NORWAY (NATIONAL REGISTRIES)	SPAIN/SIDIAP	UK/CPRD
Pregnancy feasibility counts for interim reports	Hospital-based ICD-10 codes for pregnancy related diagnoses or codes for prenatal visits from the Insurance registry for primary care prenatal visits	Hospital-based ICD-10 codes for pregnancy related diagnoses or codes for prenatal visits from the Insurance registry for primary care prenatal visits	All pregnancies in Norway that last at least 12 weeks are captured in the Medical Birth Registry of Norway (mandatory notification to the registry, 100% coverage)	Most pregnancies will be identifiable in primary care; some might be missed without linkage to hospital data	Pregnancy information will be available in the main primary care dataset following primary care and/or secondary care contact with the patient. This will be based on Read and/or SNOMED codes.
Country of residence	YES	YES	YES	YES	YES
Calendar year of delivery	YES	YES	YES	YES	YES
Pregnant woman's age	YES	YES	YES	YES	YES
Marital or cohabiting status	YES	To be verified	YES	To be verified	YES
Smoking	YES	To be verified	YES	YES	YES
Alcohol use (also ICD codes)	YES, IF BASED ON ICD CODES	YES	YES, IF BASED ON ICD CODES	To be verified	YES

Confidential

Post-marketing safety study for COVID-19 mRNA-1273 vaccine

Protocol mRNA-1273-P905, Date: 27 September 2021, Version 1.2

Marital status or other available socioeconomic measures	YES	YES	YES	YES Other available socioeconomic measures	YES
Gravidity	YES	YES	YES	YES	YES
Parity	YES	YES	YES	YES	YES

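### Preterm birth is counted per newborn although preterm status and exposure belong to the pregnancy, so without a clustered variance its 95% interval is too narrow

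*Protocol*

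**What the plan says.** Six statements in the protocol bear on this.

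- **Unit.** Section 9.7.1: "for neonatal outcomes, a newborn will be the unit of observation". The data-analysis paragraph of the abstract repeats it.
- **Outcome.** Section 9.3.2.1 lists preterm birth, a primary outcome, under adverse neonatal outcomes. Table 4 analyses it in live births, with exposure at any time during gestation.
- **Exposure.** Section 9.3.1: "The exposure will be defined by a record of receipt of at least one dose of Spikevax during pregnancy".
- **Gestational length.** Section 9.1.1 sets dates per pregnancy: "their start and end dates will be estimated based on the first day of the last menstrual period (LMP) or gestational age at end".
- **Multiples.** Section 9.2.1: "All pregnancies will be eligible for inclusion". Multifetal pregnancy appears only as a candidate covariate, in the list "placenta previa, caesarean delivery, multifetal pregnancies, prior reproductive history" (section 9.3.3) and in Table 5.
- **Model.** Section 9.7.3 plans crude and adjusted ratios from "log-binomial regression for prevalences and risks" and names no variance estimator. No section mentions clustering, robust variance or a restriction to singletons.

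**The concern.** Gestational length at delivery belongs to the pregnancy. Apart from rare delayed-interval deliveries, liveborn co-twins are both preterm or both term, and they always share the mother's vaccination status. A twin pair therefore supplies one fact about preterm birth but enters the analysis as two newborns. A log-binomial likelihood with its usual model-based variance treats them as independent.

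Twins are few, but their preterm risk is high, so they supply a large share of the preterm cases. Adjusting for multifetal pregnancy does not cure this. On the log scale a stratum carries information proportional to n·p/(1-p), which gives the high-risk twin stratum more weight than its size suggests.

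At stake is the interval for a primary safety outcome. If it is too narrow, it can suggest harm or protection where there is none, or seem to exclude a risk that it does not exclude. All sources run one common program (section 9.6), so the fault would recur in each of them.

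**Working it through.** **Planning figures.** The protocol gives no precision figure for preterm birth. Table 3 covers cardiac malformations, any major malformation, SGA and spontaneous abortion. Its first row reproduces as exp[(1.96 + z)·√((1-p)/p·(1/n₁ + 1/(5n₁)))] with n₁ = 16,667 and p = 0.01. This gives 1.27 at 80% and 1.31 at 90%, as printed. All 48 limits reproduce to within 0.005, so the planning formula takes observations as independent. The table is used below only as a source of study sizes.

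**Inputs.** From the protocol: newborn as unit, shared exposure, shared gestational length, log-binomial model, 95% level (1.96), true ratio 1. Assumed, because the protocol gives no figures:

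- t, the share of newborns who are twins: 3% (range 2-4%), that is about 1.5% (1-2%) of pregnancies
- pₛ, preterm risk in singletons: 5% (range 4.5-6%)
- pₜ, preterm risk in twins: 50% (range 40-60%)
- co-twins fully concordant for preterm status

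**From variance inflation to error rate.** If the true variance of the log ratio is D times the model-based variance, the nominal 95% interval misses a true ratio of 1 with probability 2·[1 - Φ(1.96/√D)].

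**Crude ratio.** A pair contributes a squared residual of (2r)² = 4r² for two newborns, so 2r² per newborn.

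- Overall p = 0.97×0.05 + 0.03×0.50 = 0.0635
- Singletons: 0.97×[0.05×0.9365² + 0.95×0.0635²] = 0.04625
- Twins: 2×0.03×[0.50×0.9365² + 0.50×0.0635²] = 0.02643
- D = (0.04625 + 0.02643)/(0.0635×0.9365) = 0.07268/0.05947 = 1.22
- Error rate 7.6%

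**Ratio adjusted for multifetal pregnancy.** Information per stratum is n·p/(1-p).

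- Singletons: 0.97×0.05/0.95 = 0.05105
- Twins: 0.03×0.50/0.50 = 0.03000, which is 0.03000/0.08105 = 37% of the total
- D = (0.05105 + 2×0.03000)/0.08105 = 1.37
- Error rate 9.4%

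**Range over the assumptions**

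| Model | D, central (range) | Error rate, central (range) |
|---|---|---|
| Crude | 1.22 (1.11-1.33) | 7.6% (6.3-9.0%) |
| Adjusted for multifetal pregnancy | 1.37 (1.18-1.57) | 9.4% (7.1-11.8%) |

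**Simulation.** Central assumptions, true ratio 1, 10,000 data sets per setting:

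| Births, share exposed | Crude, model-based | Adjusted, model-based | Crude, clustered | Adjusted, clustered |
|---|---|---|---|---|
| 100,000, 1/6 | 7.8% | 9.4% | 5.0% | 4.7% |
| 100,000, 1/21 | 7.4% | 9.7% | 4.7% | 5.2% |
| 20,000, 1/6 | 8.0% | 9.6% | 5.1% | 5.1% |

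**Pooled estimate.** Section 9.7.6 recommends random-effects models if a meta-analysis is done and cites DerSimonian-Laird. I simulated 400,000 meta-analyses of five sources weighted by the Table 2 births, with a true ratio of 1 and no true heterogeneity. Rejection was 5.0% at D = 1.22, 5.8% at D = 1.37 and 6.7% at D = 1.57. The between-source variance absorbs part of the understatement. With correct standard errors (D = 1) the same procedure rejects 3.7% of the time, so some inflation remains.

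**The case against.** The strongest objection is that this is SAP detail. Section 9.7 leaves the details of the analysis to the SAP, and section 9.3.2.1 leaves outcome-specific restrictions to it. A newborn-level log-binomial model with clustered standard errors would fit every sentence of sections 9.7.1 to 9.7.3 and brings the error back to about 5%. This stands in part: the protocol does not say that the variance will be model-based, so the inflation is conditional. But the unit of observation is not deferred. Section 9.7.1 states it, and its next sentence sets outcome-specific numbers at risk for malformations and stillbirth. Preterm birth is left under the general newborn rule, a poor default for a pregnancy-level outcome, with nothing said about the dependence it creates.

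Three stronger readings are tempting, and the protocol does not support them.

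- **That the error rate doubles to 10%.** This depends on assumed twin figures and on a multifetal term in the model. Section 9.7.3 calls covariates candidates that vary by database and allows a propensity score. An error of 10% needs D = 1.42, which the adjusted model reaches only in the middle-to-upper part of the range and the crude ratio nowhere.
- **That the Table 3 precision figures are wrong.** Table 3 has no preterm row. For a preterm prevalence of 0.0635 and 16,667 exposed births, the limit excluded with 80% probability moves only from 1.096 to 1.113 at D = 1.37.
- **That other neonatal outcomes are affected to a known degree.** Co-twins are not fully concordant for those outcomes, and the protocol gives no figures from which to size the effect.

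It is also fair to say that the protocol sets no significance rule for preterm birth. The consequence is interval coverage, not a formal test decision.

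**Conclusion.** The point holds, with moderate size. The protocol fixes the newborn as the unit for an outcome and an exposure that both belong to the pregnancy, keeps multifetal pregnancies, and names a model that treats newborns as independent unless a clustered variance is used. If the variance is model-based, a single-source 95% interval for preterm birth misses a true ratio of 1 about 7-12% of the time when adjusted for multifetal pregnancy and about 6-9% when crude. A DerSimonian-Laird pooled result is nearer nominal, at about 5-7%. These sizes rest on the assumed twin share and preterm risks and on full concordance of co-twins. The direction does not: any inclusion of liveborn twin pairs makes the model-based interval too narrow. The correction is worth making before the common program is written.

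**What to change.** In section 9.7.1 and Table 4, state the unit for preterm birth explicitly. Either use the delivery with at least one live birth, so that each counts once, or keep the newborn. In section 9.7.3, state that all newborn-level log-binomial models use cluster-robust (sandwich or GEE) standard errors by mother. Table 1 shows mother-child linkage in all five sources, and clustering on the mother also covers women with more than one pregnancy in the study period.

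The two choices answer slightly different questions: the proportion of deliveries that are preterm, or the proportion of newborns born preterm. The text should say which is meant. Clustered errors alone are enough to correct the interval.

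The cost is a few sentences and one option in the common program, with no new data. With the newborn as unit, the standard error on the log scale grows by √1.22 - 1 = 11% (crude) or √1.37 - 1 = 17% (adjusted) at central assumptions, and by up to √1.57 - 1 = 25%. With the delivery as unit, twin information halves to 0.0150 and the adjusted standard error is √(0.08105/0.06605) = 1.11 times the uncorrected one.

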This study is planned as analysis of routinely collected health data in secondary automated electronic data sources in Denmark, Italy, Norway, Spain, and the UK, selected based on availability of the required routinely collected data, including information on vaccine brand and frequency of data updates.

Study size

It is estimated that the number of live births available for analysis will range between 20,000 to 100,000 depending on a data source.

Data analysis

Counts and percentages will be presented for categorical variables (woman's age at conception in categories). Means, standard deviations, medians and interquartile ranges will be presented for continuous variables (woman's age at conception). The proportion of missing data will be described when appropriate. For pregnancy complications and adverse pregnancy outcomes, pregnancy will be the unit of observation; for neonatal outcomes, a newborn will be the unit of observation. For the outcomes of congenital malformations and stillbirth, the number at risk will be the total number of live or stillborn children.

Prevalence of each outcome will be computed as number of observations with a given outcome divided by the total number of observations at risk. Prevalence of each outcome will be compared for exposed vs. unexposed pregnancies according to predefined exposure categories and using, whenever necessary, plausible exposure risk windows. For example, for assessing the outcome of congenital malformations, maternal gestational diabetes and hypertensive disorders, births or pregnancies will be classified based on their exposure in the first (or second, if relevant) trimester. For all other neonatal outcomes, exposure any time in pregnancy and per trimester may be considered.

For neonatal deaths, 28-day mortality risks will be computed and compared among live-born neonates. For pregnancy-related death, maternal mortality will be evaluated at any time while pregnant or up to 1 year after pregnancy end.

All relevant analyses will be stratified by country, maternal age, sex, calendar time, trimester and seasonality if applicable.

Milestones

Data collection will continue through 31 March 2023 with a final study report planned by December 2023.

5. Amendments and updates

Write "None" or indicate any substantial amendment and update to the study protocol after the start of data collection in a table as indicated below.

Confidential

Post-marketing safety study for COVID-19 mRNA-1273 vaccine

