9.2.2 Exclusion Criteria

Excluded will be pregnancies with exposure to known teratogenic medications/infections or chromosomal anomalies (for analysis of malformations) and pregnancies with unavailable information on data on pregnancy start or end. Main analyses will be restricted to women without exposure to COVID-19 vaccines other than Spikevax during pregnancy.

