9.7.2 Measures of occurrence and measures of association

Prevalence of each outcome will be computed as number of observations with a given outcome divided by the total number of study population members. For neonatal death, a 28-day mortality risk will be the measure of occurrence among live-born infants. Prevalence/risks will be compared according to predefined exposure categories and using, whenever necessary,

plausible exposure risk windows. For example, for assessing the outcome of congenital malformations, births will be classified based on their exposure in the first trimester. For all other neonatal outcomes, exposure any time in pregnancy and per trimester may be considered.

Table 4 summarizes outcome-specific analysis populations and exposure windows.

Table 4 Summary of outcome-specific analysis populations and relevant exposure windows

Outcome	Analysis population	Relevant exposure window
Hypertensive disorders of pregnancy (preeclampsia, eclampsia, gestational hypertension)	All pregnancies	1st or 2nd trimester
Gestational diabetes	All pregnancies	1st or 2nd trimester
Bleeding during pregnancy	All pregnancies	1st or 2nd trimester
Postpartum haemorrhage	All pregnancies	Any time during pregnancy
Pregnancy-related death	All pregnancies	Any time during pregnancy
Fetal death (spontaneous abortion or stillbirth)	A combined population of stillbirths, livebirths, and pregnancies ending in a spontaneous abortion	Any time during pregnancy
Termination of pregnancy for fetal anomaly (TOPFA)	All pregnancies	Any time during pregnancy
Any elective pregnancy termination	All pregnancies	Any time during pregnancy
Ectopic pregnancy	All pregnancies	Any time during pregnancy
Fetal growth restriction/small for gestational age (SGA)	Live births	Any time during gestation
Preterm birth (<37 full gestational weeks)	Live births	Any time during gestation
Low birth weight (<2500 g)	Live births	Any time during gestation
Major congenital malformations	Live or stillbirths/TOPFA (whenever available) without evidence of teratogenic exposure or infection or chromosomal anomaly	First trimester
Microcephaly (based on head circumference)	Live births without evidence of teratogenic exposure or infection or chromosomal anomaly	Any time during gestation
Low 5-minute Apgar score	Live births	Any time during gestation
Neonatal death (death within 28 days of birth)	Live births	Any time during gestation

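### Sections 9.7.1 and 9.7.2 (Table 4) define the malformation population differently: terminations for fetal anomaly are outside one and inside the other

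*Protocol*

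**What the plan says.** Four places in the protocol bear on who is counted in the malformation analysis.

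- Section 9.7.1: "For the outcomes of congenital malformations and stillbirth the number at risk will be the total number of live or stillborn children". TOPFA is not mentioned.
- Abstract, data analysis paragraph: the same rule, "For the outcomes of congenital malformations and stillbirth, the number at risk will be the total number of live or stillborn children".
- Section 9.7.2, running text: for malformations, "births will be classified based on their exposure in the first trimester".
- Section 9.7.2, Table 4, malformation row: "Live or stillbirths/TOPFA (whenever available) without evidence of teratogenic exposure or infection or chromosomal anomaly".

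Two further statements decide what the choice of population does. Section 9.7.2 defines the measure: "Prevalence of each outcome will be computed as number of observations with a given outcome divided by the total number of study population members". Section 9.7.3 names the model as "log-binomial regression for prevalences and risks".

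Section 9.2.2 and Table 4 remove chromosomal anomalies and known teratogenic exposures or infections from the malformation analysis. TOPFA is also a primary outcome in its own right (9.3.2.1), analysed among all pregnancies.

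**The concern.** The two populations count different cases. After the stated exclusions, a termination for fetal anomaly is a small addition to the denominator, but most such terminations would be expected to be cases. Under 9.7.1 and the abstract they are outside the analysis; under Table 4 they are inside it.

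A births-only population also selects on the affected pregnancy not having been terminated. If the share of affected pregnancies that end in TOPFA differs between exposed and unexposed women, for whatever reason, the ratio among births moves away from the true one.

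Two features of the plan make it important to settle this beforehand. Section 9.6 sends one common analysis program to all data access providers, and that program can carry only one rule. Section 9.3.2.1 makes the organ-specific analyses conditional on a signal in the composite, so a shift in the composite could decide whether they are run.

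**Working it through.** **The places side by side.** Section 9.7.1 and the abstract give live-born plus stillborn children. Table 4 gives live births, stillbirths and, where available, TOPFA. Section 9.7.2 divides cases by members of the study population, and the abstract divides by observations at risk. On either wording the population fixes numerator and denominator together. A log-binomial model needs the same, because each case must be a record in the analysed data set.

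**The plan's own precision figure.** Table 3, any major malformation, largest example: 16,667 exposed, 1:5 allocation, prevalence 0.05, true ratio 1.

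- SE = sqrt[0.95/(16,667 × 0.05) + 0.95/(83,335 × 0.05)] = 0.0370
- 80% limit = exp[(1.960 + 0.842) × 0.0370] = 1.109 (table: 1.11)
- 90% limit = exp[(1.960 + 1.282) × 0.0370] = 1.127 (table: 1.13)

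Table 3 is reproduced, so its arithmetic is not in question.

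**Assumptions.** The protocol gives no TOPFA count, prevalence or share of malformation cases. Assume prevalence p = 0.05 over live births, stillbirths and TOPFA together. Let s be the share of malformation cases that end in TOPFA, and treat every TOPFA left after the exclusions as a case.

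**Cases at stake, 100,000 in total and 5,000 cases.** With s = 5%, 10% or 20%, the cases in or out number 250, 500 or 1,000. That is 0.25%, 0.5% or 1% of all records. At s = 20% the births-only prevalence is 4,000/99,000 = 4.04%.

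**Precision, births only.**

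| Table 3 example | 80% limit, TOPFA included | s = 5% | s = 10% | s = 20% |
|---|---|---|---|---|
| 16,667 exposed, 1:5 | 1.109 | 1.112 | 1.116 | 1.123 |
| 952 exposed, 1:20 | 1.500 | 1.517 | 1.535 | 1.577 |

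**Bias, births only, true ratio 1.** With shares s1 (exposed) and s0 (unexposed), the births-only prevalence is p(1 − s)/(1 − ps) in each group, so

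ratio = [(1 − s1)/(1 − p·s1)] ÷ [(1 − s0)/(1 − p·s0)].

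| s0 | s1 = s0 | s1 = 1.25 × s0 | s1 = 1.5 × s0 |
|---|---|---|---|
| 5% | 1.00 | 0.987 | 0.975 |
| 10% | 1.00 | 0.973 | 0.947 |
| 20% | 1.00 | 0.940 | 0.879 |

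For example, with s0 = 20% and s1 = 30%: (0.70/0.985) ÷ (0.80/0.990) = 0.879. In the other direction, with s1 = 10% and s0 = 20%: (0.90/0.995) ÷ (0.80/0.990) = 1.119.

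With equal shares a real effect is also preserved: a true ratio of 1.30 comes out at 1.30 for s from 10% to 20%.

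**The case against.** The best defence is that 9.7.1 names only a conventional birth denominator and that TOPFA is still counted among the cases. If that were meant, the harm would be slight: with shares of 30% and 20% the ratio under no effect would be 0.990/0.985 = 1.005. But this reading does not fit the prevalence definition in 9.7.2 or the log-binomial model, both of which need cases to be members of the population. Nor does the protocol say that it is meant.

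It can also be said that Table 4 is the designated outcome-specific summary and should prevail, that the abstract carries an older version label (draft 1.1, against the current 1.2), and that 9.3.2.1 leaves further population restrictions to the SAP. This makes Table 4 the likelier intention. It does not remove the conflict, because 9.7.1 and the running text of 9.7.2 belong to the current version and no order of precedence is given.

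TOPFA is analysed separately as a primary outcome, so differential termination could show up there. That stands, but it does not settle which population the malformation ratio uses.

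Three stronger readings are tempting and unsupported.

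- A reader might infer that a sizeable share of malformation cases is lost. The documents give no share, and terminations for chromosomal anomalies are out under either definition.
- A reader might infer that the malformation ratio will be biased towards safety. Nothing in the documents says that termination differs by vaccination; with equal shares there is no bias, and with unequal shares it can go either way.
- A reader might infer that databases with and without TOPFA will be pooled as if they measured one outcome. Section 9.7.6 reports each source separately, pools only where justifiable given differences in data flow or population, and assesses heterogeneity. Section 9.9 names uneven outcome capture as a limitation. The unevenness comes from the availability clause in Table 4 itself, not from the conflict with 9.7.1.

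**Conclusion.** The contradiction is real and unreconciled, and it concerns a primary safety outcome. Its size cannot be read from the documents.

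Under the assumptions shown (5% prevalence, TOPFA at 5-20% of unexposed cases, 1.25-1.5 times that share among exposed cases), a births-only ratio under no effect lies between about 0.99 and 0.88. It is about 1.12 with 10% in exposed and 20% in unexposed, and 1.00 with equal shares. Such a shift multiplies both ends of the interval, so the Table 3 limits do not reflect it.

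The loss of precision is minor in the largest example (80% limit 1.109 to 1.123 at a 20% share) and somewhat larger in the smallest (1.500 to 1.577). Confidence is high that the definitions conflict; the magnitudes illustrate what could follow and are not estimates. The conflict should be corrected before the common program is written.

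**What to change.** Use one population throughout. Align the abstract, 9.7.1 and the running text of 9.7.2 with Table 4: live births, stillbirths and TOPFA, after the stated exclusions, with TOPFA in both numerator and denominator in every database that can identify it. Name those databases. Keep the live-plus-stillborn denominator in 9.7.1 for stillbirth only.

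Report births-only malformation results in all databases as a sensitivity analysis, so that every source has one comparable estimate. When pooling under 9.7.6, combine only estimates that use the same population definition.

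The cost is a change of wording and one extra analysis. TOPFA is already a planned outcome, so no new data are needed.
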